APPENDIX 6: TIME PLACEMENT

TIME PLACEMENT	
A=	≤ 30 min
B=	>30 - ≤ 45 min
C=	> 45 min

APPENDIX 7: GINGIVAL STATUS

GINGIVAL STATUS	
A=	Pink, firm, free of inflammation
B=	Red and/or inflamed – no bleeding on probing
C=	Red – bleeding on probing
D=	Spontaneous and excessive bleeding on probing

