7.5.2 Preparation of the tooth

A) For NuSmile PVSCC Signature Crowns:

The tooth should be prepared to fit the crown so that the crown fits the tooth passively without using pressure. The incisal length of the tooth is reduced by approximately 2mm with the interproximal contacts opened. A feather-edge margin is created as far subgingivally as possible (approximately 1-2mm). The tooth is overall reduced by approximately 25-30%. For preparing the tooth subgingivally, and refining the preparation, tapered diamond burs may be used, proceeding from coarse to fine as the preparation is completed.

B) For NuSmile ZR Crowns:

The tooth should be prepared to fit the crown so that the crown fits the tooth passively without using pressure. The incisal length of the tooth is reduced by approximately 1.5-2mm with the interproximal contacts opened. With a coarse tapered bur, the tooth is overall reduced supragingivally by approximately 20-25%, or 0.5-1.25mm on all planes of the tooth. Reduction should follow the natural contours of the clinical crown and meet in a thin, tapered incisal edge. Carefully extend and refine the preparation margin to a feather-edge approximately 1-2mm subgingivally with a thin tapered diamond bur (green stripe 6852-012). Check that no subgingival ledges remain. Round all line angles and point angles of prepared teeth.

C) For Strip Composite Crowns:

The celluloid crown is selected based on the mesiodistal width of the tooth. The incisal length of the tooth is reduced by approximately 2mm with the interproximal contacts opened. A feather-edge margin is created supra or at gingival level. The tooth is overall reduced by approximately 15-20%. For preparing the tooth, and refining the preparation, tapered diamond or tungsten carbide burs may be used.

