10. STUDY ASSESSMENTS

Clinical Assessments will be done at baseline post crown placement; at months 3, 6, 12 and 18; and end of study visit occurring in range of 24 to 30 months from baseline.

Assessments and documentation required at each assessment interval:

• Photographs of selected teeth	Baseline
• Photographs of tooth preparations	Baseline and when possible
• Photographs of cemented crowns	Baseline
• Photographs of occlusal and frontal views	Baseline and when possible
• Assessment of fit	All intervals
• Assessment of positioning	All intervals
• Assessment of proximal contact	All intervals
• Assessment of marginal adaptation	All intervals
• Assessment of color: match , staining/color change	All intervals
• Assessment of time placement	Baseline
• Assessment of gingival status	All intervals
• Assessment of retention	3, 6, 12, 18 and 24 mo
• Assessment of veneer/composite integrity	3, 6, 12, 18 and 24 mo
• Assessment of secondary caries	3, 6, 12, 18 and 24 mo
• Assessment of trauma	3, 6, 12, 18 and 24 mo
• Assessment of clinical pulp pathology	3, 6, 12, 18 and 24 mo
• Assessment of radiographic pulp pathology	24 mo
• Assessment of tooth	All intervals
• Assessment of parents' esthetic satisfaction	All intervals (baseline at 3-month follow up)

Non-recall assessment to be done at the time of tooth/crown lost to study due to trauma. If this was to occur, the patient would be discontinued from study and the justification recorded.

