11.0 DATA ANALYSIS

Descriptive statistics (means, standard deviations, counts, and percentages) will be calculated for all variables. To evaluate if the primary efficacy variables differ by the three treatment groups (NuSmile PVSCC Signature Crowns, NuSmile ZR, and Strip composite crowns), ANOVA or Chi-square tests of association will be performed.

All subjects evaluated at the 6-month interval or beyond and subjects who have lost crowns or teeth will be considered for efficacy. All enrolled subjects defined here as those who have had at least one crown placed will be evaluated for safety. Any missing, unused or false data will be omitted from data analysis.

The primary efficacy variables in this trial are fit, positioning, proximal contact, marginal adaptation, color match, gingival status, crown retention, veneer/composite integrity, secondary caries, occlusal integrity, history of trauma, clinical pulp pathology, parents' esthetic satisfaction. Scores for efficacy variables will be summarized and displayed using descriptive statistics (means, standard deviations, counts, and percentages).

Inferential statistics will be used to detect significant differences in the primary efficacy variables by the treatment status at baseline and at 6, 12, 18, and 24 month follow-up. Statistical differences will be calculated using logistic regression models accounting for within cluster variance using generalized estimating equations (GEE).

Safety variables include Adverse Events and Unanticipated Adverse Device Effects. All subjects that have had crowns placed will be evaluated for safety. Descriptions of occurrences, incidence, severity and required treatments for Adverse Events and Unanticipated Adverse Device Effects Will be summarized and tabulated where appropriate.

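### The gingival scale in Appendix 7 is neither exhaustive nor exclusive: one tissue state has no grade, pink tissue that bleeds scores A, and grade D overlaps C

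*Combined protocol and SAP*

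**What the plan says.** Appendix 7 gives four grades:

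- The best grade, A, reads "Pink, firm, free of inflammation".
- One step down from it, grade B reads "Red and/or inflamed – no bleeding on probing".
- The next step down, grade C, reads "Red – bleeding on probing".
- The worst of the four, grade D, reads "Spontaneous and excessive bleeding on probing".

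It has no rule for tissue that fits two grades or none, and does not define *excessive*.

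Section 11.0 places the variable in its primary list ("marginal adaptation, color match, gingival status, crown retention" is part of that list of 13). Section 10 schedules "Assessment of gingival status" at all intervals. Section 11.0 plans ANOVA or chi-square tests and logistic GEE models, but does not say how four grades become a binary outcome. Section 7.1 asks for intra- and inter-reliability with Kappa above 0.8, without naming the scales covered. Section 4 describes the trial as non-blinded. In Section 7.5.2 both NuSmile crowns have margins about 1–2 mm below the gingiva; for the strip crown, "A feather-edge margin is created supra or at gingival level".

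**The concern.** The grades mix three signs (colour, inflammation, bleeding) but do not carry the same conditions from one grade to the next. B accepts inflammation without redness; C does not. A excludes inflammation but says nothing about bleeding. D has no colour condition and joins two different bleeding signs. A rater who meets a state that the wording does not settle must supply a rule, and the document does not record which one.

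At stake is the grade distribution of a primary variable. If raters settle these states differently, the share graded healthy depends partly on the rater. Because the trial is not blinded, the choice could also vary with the arm.

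**Working it through.** The plan states no figure on this point, so there is none to reproduce. The check is an enumeration of the wording, followed by two illustrations on assumed rates.

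**Enumeration.** Cross redness (yes/no), inflammation (yes/no), bleeding on probing (none/ordinary/excessive) and spontaneous bleeding (yes/no). Omit spontaneous bleeding without bleeding on probing. That leaves 2 × 2 × 5 = 20 states. Match each literally to Appendix 7, taking pink as not red. In each cell, the left of the arrow reads D as needing both signs, the right as needing either.

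| Bleeding | Not red, not inflamed | Not red, inflamed | Red (inflamed or not; counts as two states) |
|---|---|---|---|
| None | A → A | B → B | B → B |
| Ordinary on probing | A → A | no grade → no grade | C → C |
| Ordinary, plus spontaneous | A → A or D | no grade → D | C → C or D |
| Excessive on probing | A → A or D | no grade → D | C → C or D |
| Excessive, plus spontaneous | A or D → A or D | D → D | C or D → C or D |

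- D needs both: 3 states fit no grade; 1 (A/D) + 2 (C/D) = 3 fit two; 20 − 3 − 3 = 14 fit exactly one.
- D needs either: 1 state fits no grade; 3 (A/D) + 6 (C/D) = 9 fit two; 20 − 1 − 9 = 10 fit exactly one.

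The state without a grade under both readings is non-red, inflamed tissue with ordinary bleeding on probing. These are counts of states, not frequencies in patients.

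**Which analyses are touched.** Confusion between C and D changes a four-category chi-square or a scored ANOVA. It cannot change a binary outcome cut at A versus B–D or at A/B versus C/D. The ungraded state can change an A/B versus C/D cut, and an A versus B–D cut if a rater enters A. The A/D states can change either cut.

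**Illustration 1: agreement (all rates assumed).** A fraction f of crowns is entered as A by one rater and C by another. They agree on the rest, spread 60/20/15/5% over A–D. At f = 10%:

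- Share graded A: 0.9 × 0.60 + 0.10 = 0.64 versus 0.9 × 0.60 = 0.54. Observed agreement is 0.90.
- A versus B–D: chance agreement 0.64 × 0.54 + 0.36 × 0.46 = 0.5112; kappa = (0.90 − 0.5112)/(1 − 0.5112) = 0.795.
- Four grades, unweighted: chance agreement 0.64 × 0.54 + 0.18² + 0.135 × 0.235 + 0.045² = 0.4118; kappa = 0.83.
- A/B versus C/D: chance agreement 0.82 × 0.72 + 0.18 × 0.28 = 0.6408; kappa = 0.72.
- Linear-weighted kappa: 0.79.

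At f = 5% all four exceed 0.8 (A versus B–D: 0.897). At f = 15% and 20%, A versus B–D gives 0.698 and 0.606; the unweighted four-grade kappa at 15% is 0.75.

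**Illustration 2: power (all rates assumed).** Take C/D rates of 20% versus 50%, 30 independent subjects per arm and two-sided 0.05. Power = Φ[(|p₂ − p₁| − 1.96·SE₀)/SE₁], where SE₀ uses the pooled proportion and SE₁ the separate ones. With no misgrading: SE₀ = √(2 × 0.35 × 0.65/30) = 0.1232, SE₁ = √((0.16 + 0.25)/30) = 0.1169, power 0.69. If 5%, 10% or 20% of C/D cases in both arms are entered as A/B, power is 0.66, 0.62 or 0.55.

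**The case against.** The strongest reply is that a sensible rater would manage. If bleeding on probing is itself taken as a sign of inflammation, A is excluded, B is excluded by its own wording, and C is the nearest grade. Section 7.1 also plans training and calibration with a Kappa target. The variable is one of 13 in a pilot with a convenience sample of 90, and no design figure depends on it.

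Much of this stands. C is probably what most raters would choose, which makes the A-versus-C split in Illustration 1 an extreme case. Calibration should limit disagreement, but only in part: the gingival scale is not named and no tie-break is given. Raters can also agree on a rule that a reader cannot reconstruct.

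A reader might infer more than the text supports:

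- *That no non-red bleeding tissue has a grade.* D has no colour condition and A does not exclude bleeding, so several such states do have one.
- *That agreement will miss the 0.8 target.* That rests on an assumed f and on a choice of kappa that the plan does not make; at f = 10% the four-grade kappa passes.
- *That the comparison is biased by arm.* The margin depths do differ, but nothing in the documents shows that the ambiguous states are commoner in one arm.

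**Conclusion.** The defect holds as a fault in the wording of a stated scale. It has three parts: a gap (inflamed, non-red, ordinary bleeding on probing), a literal A for pink, uninflamed tissue that bleeds, and a grade D that can be read two ways and overlaps C. Only the first is a gap, and only the third is an overlap between adjacent grades.

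Its effect on results cannot be sized from the documents. They give no frequency for any of these states, no cut-point for the logistic model and no type of kappa. The kappa and power figures above show a possible range under assumed rates and are not estimates for this trial. Severity is minor. It is still worth correcting, because the variable is listed as primary, is scored at all intervals, and the trial is not blinded.

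**What to change.** Reword Appendix 7 so that bleeding decides first, and record the highest grade that applies:

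- A: pink and firm, with neither inflammation nor bleeding on probing.
- B: redness, inflammation or both, without bleeding on probing.
- C: bleeding on probing only, whatever the colour.
- D: spontaneous bleeding, that is, bleeding without probing.

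Applied to the 20 states, this gives 1 in A, 3 in B, 8 in C and 8 in D, which sums to 20 with none unplaced or doubled. Use the same wording on the case report form, name this scale in the calibration under Section 7.1, and state in Section 11.0 the cut-point at which the four grades enter the logistic GEE model.

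The cost is an edit to one appendix and one form before scoring, plus a sentence each in Sections 7.1 and 11.0; no extra visit or staff. The downside is that C becomes broader: excessive but non-spontaneous bleeding on probing moves from D to C, so scores are slightly less comparable with those under the present Appendix 7. The border between A and B still needs a judgement of redness and inflammation, and the rewording does nothing about the lack of blinding.

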APPENDIX 8: RETENTION

RETENTION	
A=	Intact
B=	Partially missing
C1=	Missing – no cement remaining on tooth or crown
C2=	Missing – some or all cement remaining on tooth
C3=	Missing – some or all cement remaining on crown interior (if crown available)
C4=	Missing – some cement remaining on both tooth and crown interior (if crown available)

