7.5.3 Crown Fitting, Adjustment and Cementation

A) For NuSmile PVSCC Signature Crowns:

In some cases, shortening the crown from the gingival margin may be necessary to achieve the desired results. The NuSmile Shortening Bur may be used at low range speed with a water spray to circumferentially reduce and feather the crown margins. After shortening, the composite polisher may be used to restore a polished surface to the esthetic facing.

A properly fitted crown will have a passive fit and be seated with finger pressure only. A "snap fit" is both undesirable and counter-productive as it may result in failure of the veneer. If the crown does not fit passively, the preparation must be refined to fit the crown. Crimping is not necessary, but if needed, excessive crimping or crimping near the facing must be avoided.

Clean the teeth of saliva, blood or debris and control gingival hemorrhage. NuSmile's Bio-active Resin Modified Glass Ionomer Cement will be used to cement the crowns according to the manufacturer's directions for use.

Once seated and after allowing enough time for the cement to set, a white stone or composite finishing bur may be used to equilibrate the veneer out of excessive occlusal contact in centric and excursion functions. The opposing teeth may be slightly adjusted, if needed.

It may be desirable to trim the veneer flush with the incisal edge if the patient demonstrates bruxism patterns or end-on occlusion. The distal point angle may be rounded to shape the crown for a right or left anterior.

B) For NuSmile *ZR* crowns:

Use NuSmile *Try-In* Crowns to test the fit and to avoid contamination with saliva or blood of NuSmile *ZR* Crown's prepared internal surface. If contamination with saliva or blood occurs, clean the internal surface of the NuSmile *ZR* Crown with Ivoclean or sandblast with aluminum oxide.

A properly fitted crown will have a passive fit and be seated with finger pressure only. A "snap fit" is both undesirable and counter-productive as it may result in fracture of the crown. If the crown does not fit passively, the preparation must be refined to fit the crown.

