NuSmile *ZR* Crowns should only be adjusted with burs specifically designed for adjusting zirconia restorations taking care to use a light touch and a copious water spray. The NuSmile *ZR* Adjustment Burs can be used to circumferentially reduce and feather the crown margins when shortening a crown is necessary. The crown walls are very thin and should not be adjusted any more than 0.5mm in the incisal ½ of the proximal area as necessary. No other areas of the crowns should be adjusted. If adjustments are made, the *ZR* polishers should be used to restore a smooth surface to the crown.

Clean the teeth of saliva, blood or debris and control gingival hemorrhage. NuSmile's Bio-active Resin Modified Glass Ionomer Cement will be used to cement the crowns according to the manufacturer's directions for use.

C) For Strip Composite Crowns:

Trim the crown form and pierce one hole in the palatal incisal angle with a high-speed bur. Etch the enamel for approximately 20 seconds, wash and dry without desiccation of the dental structures. Apply a thin layer of bonding resin cure for 20 seconds ensuring that all surfaces are bonded equally. Fill celluloid crown with the appropriate shade of composite and seat with gentle, even, pressure, allowing excess to exit freely. Light-cure each tooth surface (labially, incisally and palatally) equally. Remove celluloid crown gently and adjust form and finish with either composite finishing burs or abrasive discs.

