APPENDIX 9: VENEER/COMPOSITE INTEGRITY

VENEER/COMPOSITE INTEGRITY	
A=	Intact
B1=	Partially missing – one third missing
B2=	Partially missing – two thirds missing
B3=	Partially missing – more than two thirds missing
C4=	All veneer/composite missing

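### Retention grade B overlaps the integrity scale and the cement subcodes do not fit strip crowns, so unless retention is tested as missing versus present, arms can differ with equal crown loss

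*Combined protocol and SAP*

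**What the plan says.** Appendix 8 has one retention scale for every arm. A is intact, B is "Partially missing", and C1 to C4 are grades of a missing crown that differ only in where cement is found; C1 reads "Missing – no cement remaining on tooth or crown". Grade B does not say which material is missing, or how much.

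Appendix 9 grades the veneer or composite. Its partial grades start with "Partially missing – one third missing" and its last grade is "All veneer/composite missing".

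The three crowns are built and fixed differently. Section 1 describes the Signature crown as a steel crown with a bonded composite facing, and the ZR crown as monolithic zirconia. For both of these, Section 7.5.3 says "NuSmile's Bio-active Resin Modified Glass Ionomer Cement will be used to cement the crowns". For the strip crown the same section gives etching, bonding resin and then: "Fill celluloid crown with the appropriate shade of composite and seat with gentle, even, pressure, allowing excess to exit freely". The celluloid form is then removed, so the composite is the whole restoration. No cementation step is given.

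Section 11.0 lists the two scales as separate primary efficacy variables ("color match, gingival status, crown retention, veneer/composite integrity, secondary caries"). It plans chi-square tests or ANOVA, and logistic regression with GEE. It gives no cut-point for either scale and does not say which scale takes a partial loss.

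**The concern.** A retention comparison is normally read as showing which crowns stay on the tooth. Here the middle grade can record breakage of material in a crown that is still in place, and whether it does so depends on how the crown is built. The same kind of event may count under two primary variables in the control arm, under one in the Signature arm, and under the other in the ZR arm. The grades for a lost crown also rest on a material that one arm does not use.

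A logistic model needs a binary outcome, and treating anything other than A as failure is an obvious choice that the plan does not rule out. With that choice, or with a chi-square test across all the levels, a difference in chipping or in cement coding can be reported as a difference in retention.

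**Working it through.** **Step 1. Is there a figure in the plan to reproduce?** No. The sample size of 90 (3 × 30) is a convenience sample with no effect size, alpha or power. The check is therefore a mapping of events onto the two scales, followed by an illustration.

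**Step 2. Mapping, from Section 1, Section 7.5.3 and Appendices 8 and 9.**

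| Event | Retention (App. 8) | Integrity (App. 9) |
|---|---|---|
| Strip crown chipped | B fits | B1 to B3 fit |
| Signature facing chipped, shell in place | A on the natural reading; B not ruled out | B1 to B3 fit |
| ZR crown partly fractured | B is the only fit | nothing to grade (no veneer or composite) |
| Strip crown lost | missing; C1 by default, C2 to C4 do not fit | C4 also fits |
| Signature or ZR crown lost | C1 to C4 | not addressed |

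Under Section 7.5.4 a tooth that cannot take its allocated crown receives a composite crown and stays in the study by intention to treat. The strip-crown coding problem can therefore also arise in the two NuSmile arms.

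**Step 3. Which analyses are affected?**

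- Missing (C1 to C4 pooled) versus present (A or B): unaffected. All four C codes mean the crown is missing, and grade B falls on the present side.
- Anything other than A as failure: affected through grade B.
- Chi-square across the levels as written: affected through grade B, and also through the subcodes, because lost strip crowns default to C1 while lost cemented crowns can spread over C1 to C4.

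**Step 4. Illustration.** The documents give no rates, so all rates here are assumed. Let L be true whole-crown loss, equal in the strip and Signature arms, and c the share of retained strip crowns that are chipped and graded B. Signature chips are graded A on retention. With failure defined as B or C:

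- Signature: p1 = L
- Strip: p2 = L + (1 − L) × c
- Apparent gap: (1 − L) × c

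The chance of a significant result uses the usual normal approximation for two proportions: 30 per arm, two-sided 0.05, one crown per child. For L = 5% and c = 20%:

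- p2 = 0.05 + 0.95 × 0.20 = 0.24, so the gap is 0.19; the pooled rate is 0.145.
- Null standard error = √(0.145 × 0.855 × 2/30) = 0.0909.
- Alternative standard error = √((0.05 × 0.95 + 0.24 × 0.76)/30) = 0.0875.
- Φ((0.19 − 1.96 × 0.0909)/0.0875) = about 55%.

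| c (with L = 5%) | p2 | Gap, B or C as failure | Chance of significance | Gap, C1 to C4 pooled |
|---|---|---|---|---|
| 5% | 9.8% | 4.8 points | 10% | 0 |
| 10% | 14.5% | 9.5 points | 23% | 0 |
| 20% | 24.0% | 19.0 points | 55% | 0 |
| 30% | 33.5% | 28.5 points | 82% | 0 |

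With L from 2% to 10% and the same values of c, the chance runs from about 8% to about 88%. The calculation ignores clustering of up to four crowns per child.

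**The case against.** The strongest reply is that the data needed are already collected. Pooling C1 to C4 gives crown present or absent in every arm, whatever happens to grade B or the cement codes. That stands. A reader might infer that the trial cannot tell which crown stays on the tooth; Appendix 8 does not support this.

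A reader might also infer that retention is biased against the strip-crown control as planned. The documents do not support that either. They set no failure threshold, so double counting is possible but not prescribed, and an examiner could grade a Signature chip B as well. The cement wording cannot alter a lost versus not-lost comparison; it matters only if the levels or subcodes are tested.

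It can further be said that an intact, partial and missing scale is a permissible choice, and that losing part of an all-composite crown differs in kind from losing a facing over a cemented shell. That is fair, and is a reason to keep partial loss on record. It does not justify an unstated rule on how partial loss enters a retention test.

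The gaps in the illustration largely return the assumed chipping rate, so they show how the cut-point acts and predict nothing. This is also a pilot, but Section 11.0 still plans inferential tests on these variables. The kappa target in Section 7.1 concerns agreement between and within examiners; it does not make grade B mean the same thing for three kinds of crown.

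**Conclusion.** The concern holds in a limited form. Grade B of Appendix 8 overlaps Appendix 9 in a way that differs by crown type, and the C1 to C4 subcodes are not comparable between cemented and bonded crowns. If the chi-square test is run on the levels as written, or the logistic model counts anything other than A as failure, the arms can differ on retention while whole-crown loss is equal.

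The size depends on chipping rates that the documents do not give. Under the assumptions above it is 4.8 to 28.5 points at 5% true loss, and zero under a missing-versus-present endpoint. The choice of cut-point alone can create or remove the difference, so it should be stated in the plan.

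A reader might conclude that grade B should simply be deleted. Appendix 9 as worded has no grade for fracture of a monolithic ZR crown, an event that Section 7.5.3 itself mentions. Deleting B without other changes would leave that event with no grade on either scale.

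**What to change.** 1. In Section 11.0, define the retention endpoint as missing (C1 to C4 pooled) versus present (A or B), and use this definition in both the chi-square test and the logistic GEE model.
2. Do not test the cement subcodes across arms. Keep them as a descriptive field for cemented crowns, with a not-applicable entry for strip crowns, including composite crowns placed after a failure to fit under Section 7.5.4.
3. Count partial loss or fracture once, under integrity, and reword Appendix 9 to cover fracture of the ZR crown. The same rewording should say whether a lost strip crown is also graded there.
4. If Appendix 9 is not reworded, keep grade B as a recorded, descriptive level so that ZR fracture is not lost.

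The cost is one definition in Section 11.0 and edits to Appendices 8 and 9, with no new assessment. The downside is that partial loss no longer counts as retention failure, but it is still reported.
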